Table 3.5-1 Schedule of Subject Evaluations for Subjects Receiving Single IV Doses of MEDI-546 (Dose Cohorts 1-5, and 9)

Evaluations	Study Day								
	Screening (-28 to -1)	0	1	7	14	21	28	56	84/Discont ^a
Viral Cultures		X					X	X	X
Safety Biomarkers		X							
DISEASE ACTIVITY AND PATIENT-REPORTED OUTCOMES									
HAQ-DI With Scleroderma NRS		X					X	X	X
Modified Rodnan Total Skin Score		X					X	X	X
European Disease Activity Index		X					X	X	X
ESR, CRP, Serum Complement C3 & C4		X					X	X	X
Autoantibody Levels		X					X	X	X
PK/IM/PD									
MEDI-546 Serum Concentration		X ^b	X	X	X	X	X	X	X
Anti-MEDI-546 Antibodies		X ^c					X	X	X
Whole Blood for Receptor Occupancy Analysis		X ^b	X	X	X	X	X	X	X
Whole Blood for Type I IFN-inducible Genes, Exploratory Analyses & Storage		X ^c	X	X	X		X	X	X
Skin Biopsy for Type I IFN-inducible Genes and Exploratory Studies		X ^c		X					

Table 3.5-1 Schedule of Subject Evaluations for Subjects Receiving Single IV Doses of MEDI-546 (Dose Cohorts 1-5, and 9)

Evaluations	Study Day								
	Screening (-28 to -1)	0	1	7	14	21	28	56	84/Discont ^a
CORRELATIVE STUDIES									
Serum for Exploratory Correlative Studies & Storage		X ^c	X	X	X		X	X	X
DNA Sample (optional) ^c		X							

^a These evaluations will be performed in subjects who discontinue the study prematurely, unless the evaluation was performed within 2 weeks of the discontinuation visit, or in the case of repeat skin biopsy, if it was done at Study Day 7.

^b Samples will be collected predose and 0.5 hours post end of infusion.

^c Samples will be collected predose.

Table 3.5-2 Schedule of Subject Evaluations for Subjects Receiving Multiple IV Doses of MEDI-546 (Dose Cohorts 6-8)

Evaluations	Study Day										
	Screening (-28 to -1)	0	1	7	14	21	22	28	56	84	105/Discont ^a
Written Informed Consent and HIPAA (for US sites only)	X										
Verify Eligibility Criteria	X	X									
Medical History	X	X									
Physical Examination	X	X						X			X
ECG	X										X
Chest X-ray	X										
Pulmonary Function Tests	X							X	X	X	X
TB Skin Test	X										
Hepatitis A,B,C; HIV-1,-2	X										
Serum βHCG	X										
Urine βHCG		X		X	X	X					X
MEDI-546 ADMINISTRATION		X		X	X	X					
SAFETY ASSESSMENT											
Vital Signs	X	X	X	X	X	X	X	X	X	X	X
AE/SAE Assessment	X	X	X	X	X	X	X	X	X	X	X
Record Concomitant Medications	X	X	X	X	X	X	X	X	X	X	X
Serum Chemistry	X	X		X	X	X		X	X	X	X
Hematology	X	X		X	X	X		X	X	X	X

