Note: Items 4 and 5 above are designed to collect information on the subject once enrolled into the study and start the screening process. Any new physical exam finding, symptom, disease, or untoward medical event that begins after written informed consent has been obtained, but before receipt of investigational product, that is not related to a protocol requirement must be added to the baseline medical history or physical exam.
- 6) Perform ECG
- 7) Perform chest x-ray (anterior/posterior and lateral)
Note: The chest x-ray may be substituted with documentation of a previous chest x-ray performed within the previous 6 months. A previous computerized tomography evaluation of the lungs may be substituted for the chest x-ray if performed within the last 6 months.
- 8) Perform pulmonary function tests
- 9) Perform TB skin test
- 10) Monitor for vital signs (includes temperature, blood pressure, pulse rate, respiratory rate)
- 11) Assess for SAEs and protocol-related AEs
- 12) Record concomitant medications
- 13) Collection of blood and urine
 - Serum for hepatitis A antibody, hepatitis B surface antigen, hepatitis C antibody, and HIV-1 and HIV-2 antibody
 - Serum β human chorionic gonadotropin (β HCG)

- Serum chemistry (includes sodium, potassium, chloride, bicarbonate, blood urea nitrogen, creatinine, ALT, AST, bilirubin, alkaline phosphatase, and glucose [random])
- Hematology (includes CBC with differential and platelet count and hemoglobin)
- Urinalysis

Study Day 0

All Dose Cohorts

- 1) Verify eligibility criteria
- 2) Update screening history and physical examination (any new findings since screening)
- 3) Monitor vital signs
- 4) Assess for SAEs and protocol-related AEs
- 5) Update concomitant medications
- 6) Collection of blood, urine, and cultures (all prior to MEDI-546 administration and may be done up to 72 hours prior to dosing, except urine β HCG which must be on day of dosing)
 - Urine β HCG
 - Serum chemistry
 - Hematology
 - Urinalysis
 - Viral cultures
 - Safety biomarkers
 - Erythrocyte sedimentation rate (ESR), cross-reactive protein (CRP), serum complement C3, C4
 - Autoantibody levels (includes ANA, anti-topoisomerase I (anti-Sc170), and anti-centromere antibodies and potential assessment of anti-fibroblast and anti-endothelial cell antibodies)
 - MEDI-546 serum concentration
 - Receptor occupancy analysis
 - Type I IFN-inducible genes, exploratory analyses, and storage
 - Anti-MEDI-546 antibodies

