- 9) Monitor vital signs about every 15 minutes during infusion, immediately after the end of the infusion, and about every 30 minutes after the end of the infusion for 2 hours or until stable, whichever is later. Monitor blood pressure and heart rate prior to discharge from the study site.
- 10) Monitor for AEs and SAEs

Study Day 14 (\pm 2 days)

All Dose Cohorts

- 1) Monitor vital signs
- 2) Monitor for AEs and SAEs
- 3) Record concomitant medications
- 4) Collection of blood and urine prior to MEDI-546 administration, if applicable

- Serum chemistry
- Hematology
- Urinalysis
- MEDI-546 serum concentration
- Receptor occupancy analysis
- Type I IFN-inducible genes, exploratory analyses, and storage
- Exploratory correlative studies and storage (serum)

Dose Cohorts 6-8 only

- 5) Urine β HCG before MEDI-546 administration
- 6) Monitor vital signs within 60 minutes before administration of MEDI-546
- 7) **Administration of MEDI-546**
- 8) Monitor vital signs about every 15 minutes during infusion, immediately after the end of the infusion, and about every 30 minutes after the end of the infusion for 2 hours or until stable, whichever is later. Monitor blood pressure and heart rate prior to discharge from the study site.
- 9) Monitor for AEs and SAEs

Study Day 21 (\pm 2 days)

All Dose Cohorts

- 1) Monitor vital signs
- 2) Monitor for AEs and SAEs
- 3) Record concomitant medications
- 4) Collection of blood and urine prior to MEDI-546 administration, if applicable
 - Serum chemistry
 - Hematology
 - Urinalysis
 - MEDI-546 serum concentration
 - Receptor occupancy analysis

Dose Cohorts 6-8 only

- 5) Urine β HCG before MEDI-546 administration
- 6) Monitor vital signs within 60 minutes before administration of MEDI-546

- 7) **Administration of MEDI-546**
- 8) Monitor vital signs about every 15 minutes during infusion, immediately after the end of the infusion, and about every 30 minutes after the end of the infusion for 2 hours or until stable, whichever is later. Monitor blood pressure and heart rate prior to discharge from the study site.
- 9) Blood collection at 0.5 hour post end of infusion
 - MEDI-546 serum concentration
 - Receptor occupancy
- 10) Monitor for AEs and SAEs

Study Day 22 (\pm 2 days)

Dose Cohorts 6-8 only

- 1) Monitor vital signs
- 2) Monitor for AEs and SAEs
- 3) Record concomitant medications
- 4) Collection of blood
 - MEDI-546 serum concentration
 - Receptor occupancy analysis

Study Day 28 (\pm 2 days)

All Cohorts

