- 1) Perform physical examination
- 2) Perform pulmonary function tests
- 3) Monitor vital signs
- 4) Monitor for AEs and SAEs
- 5) Record concomitant medications
- 6) Collection of blood, urine, and cultures
 - Serum chemistry
 - Hematology
 - Urinalysis
 - Viral cultures
 - ESR, CRP, serum complement C3, C4

- Autoantibody levels
 - MEDI-546 serum concentration
 - Receptor occupancy analysis
 - Type I IFN-inducible genes, exploratory analyses, and storage
 - Anti-MEDI-546 antibodies
 - Exploratory correlative studies and storage (serum)
- 7) Assess HAQ-DI with scleroderma NRS (preferably performed prior to mRTSS and European DAI)
 - 8) Assess mRTSS
 - 9) Assess European DAI

Dose Cohorts 6-8 only

- 10) Skin biopsy for type I IFN-inducible genes and exploratory studies

Study Day 56 (± 4 days)

All Dose Cohorts

- 1) Perform pulmonary function tests
- 2) Monitor vital signs
- 3) Monitor for AEs and SAEs
- 4) Record concomitant medications
- 5) Collection of blood, urine, and cultures
 - Serum chemistry
 - Hematology
 - Urinalysis
 - Viral cultures
 - ESR, CRP, serum complement C3 & C4
 - Autoantibody levels
 - MEDI-546 serum concentration
 - Receptor occupancy analysis
 - Type I IFN-inducible genes, exploratory analyses, and storage
 - Anti-MEDI-546 antibodies
 - Exploratory correlative studies and storage (serum)

- 6) Assess HAQ-DI with scleroderma NRS (preferably performed prior to mRTSS and European DAI)
- 7) Assess mRTSS
- 8) Assess European DAI with Patient Reported Outcomes

Study Day 84 (\pm 7 days) or Study Discontinuation for Dose Cohorts 1-5 and 9

If a subject in Dose Cohorts 1-5 and 9 discontinues the study prematurely prior to Study Day 84, he or she should return to the study site and complete the following evaluations. If a particular assessment has been performed within 2 weeks before the discontinuation visit, it need not be repeated.

All Dose Cohorts

- 1) Perform pulmonary function tests
- 2) Monitor vital signs
- 3) Monitor for AEs and SAEs
- 4) Record concomitant medications
- 5) Collection of blood urine, and cultures
 - Serum chemistry
 - Hematology
 - Urinalysis
 - Viral cultures
 - ESR, CRP, serum complement C3, C4
 - Autoantibody levels
 - MEDI-546 serum concentration
 - Receptor occupancy analysis
 - Type I IFN-inducible genes, exploratory analyses, and storage
 - Anti-MEDI-546 antibodies
 - Exploratory correlative studies and storage (serum)

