3.7 Completion of Study, Discontinuation of Study, and Loss to Follow-up

Subjects enrolled in Dose Cohorts 1-5 and 9 will be considered to have completed the study if they were followed through Study Day 84. Subjects enrolled in Dose Cohorts 6-8 will be considered to have completed the study if they were followed through Study Day 105. Multiple ascending dose cohorts (Cohorts 6, 7, 8) and single ascending dose cohorts (Cohort 9) will enroll simultaneously; End of Study is defined as the last subject last visit for either cohort 8 (Day 105/Discontinuation) or Cohort 9 (Day 85/Discontinuation) whichever comes later. If a subject discontinues prior to the end of study it should be specified on the source document when the subject discontinued and the reason for discontinuing the study early. If a subject discontinues his or her participation in the study prior to Study Day 84 for Dose Cohorts 1-5 and 9 and Study Day 105 for Dose Cohorts 6-8, the subject will return to the study site and complete the Study Discontinuation Visit evaluations. If a particular assessment has been performed within 2 weeks prior to the discontinuation visit, it need not be repeated. Repeat skin biopsies should be obtained if not already done.

Subjects will be considered lost to follow-up only if no contact has been established by the time the study is completed such that there is insufficient information to determine the

subject's status at Study Day 84 (Dose Cohorts 1-5 and 9) or Study Day 105 (Dose Cohorts 6-8, . Investigators or qualified designees should document attempts to re-establish contact with missing subjects throughout the study period. If contact with a missing subject is re-established, follow-up should resume according to the protocol.

4 Safety Assessment

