5.4 Primary Endpoints

The safety and tolerability of MEDI-546 will be assessed primarily by summarizing treatment-emergent AEs and SAEs and by assessing changes in viral cultures, including oropharyngeal swabs for HSV-1 and HSV-2; vaginal swabs for HSV-1, HSV-2, and HPV; and peripheral blood test for EBV and CMV (using molecular assays). The occurrence of treatment-emergent AEs and SAEs will be summarized from the period immediately following the first administration of MEDI-546 through end of study (Study Day 84 for subjects receiving single IV doses and Study Day 105 for subjects receiving multiple IV doses). Treatment-emergent AEs and SAEs will be summarized by system organ class and

preferred terms, by severity, and by relationship to MEDI-546. Treatment-emergent AEs and SAEs will be summarized for each of the MEDI-546 dose cohorts, and for all MEDI-546 dose cohorts combined.

No formal statistical testing will be performed to compare treatment groups. Other variables used for the safety assessments include serum chemistry, CBC with differential and platelets, and urinalysis. These variables as well as their changes from baseline will be summarized descriptively.

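### The 2-week waiver at the study-discontinuation visit does not require the earlier sample to follow dosing, so a pre-infusion sample can stand in for the exit labs, viral tests and antibody sample

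*Protocol*

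**What the plan says.** The waiver appears in five places in the protocol, and none of them requires that the earlier assessment follow dosing.

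- Section 3.5, the discontinuation visit for Cohorts 1-5 and 9 (with Day 84) and for Cohorts 6-8 (with Day 105), in the same words both times: "If a particular assessment has been performed within 2 weeks before the discontinuation visit, it need not be repeated".
- Footnote a of Tables 3.5-1 and 3.5-2: "These evaluations will be performed in subjects who discontinue the study prematurely, unless the evaluation was performed within 2 weeks of the discontinuation visit". The footnote makes one exception, for the repeat skin biopsy.
- Section 3.7: "If a particular assessment has been performed within 2 weeks prior to the discontinuation visit, it need not be repeated". It adds that a repeat biopsy is to be taken if none has been done.

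The timing of the samples is set in Section 3.5.

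- Day 0, all cohorts: "Collection of blood, urine, and cultures (all prior to MEDI-546 administration and may be done up to 72 hours prior to dosing". This list includes chemistry, hematology, urinalysis, viral cultures and anti-MEDI-546 antibodies. For the antibody sample, footnote c of the tables repeats the point: "Samples will be collected predose".
- Days 7, 14 and 21: "Collection of blood and urine prior to MEDI-546 administration, if applicable". In Cohorts 6-8 these are infusion days.
- After Day 0, viral cultures and antibodies are next scheduled on Day 28 in both tables.

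Section 5.4 makes "assessing changes in viral cultures" part of the primary safety assessment. Section 5.5.2 summarizes the number and percentage of subjects who develop antibodies. Section 5.3 keeps every dosed subject in all summaries and imputes nothing.

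**The concern.** An exit visit in a first safety study should show the subject's state after exposure. A waiver based only on elapsed days lets a sample drawn before the infusion serve as the exit sample. The subject then has a baseline and nothing to compare it with.

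Three uses of these data are affected. Viral change cannot be computed without a post-dose result. A pre-dose antibody sample cannot show antibodies induced by treatment, yet Section 3.4.4 uses measurable antibodies to separate anaphylaxis from infusion reactions, and Section 3.5 allows antibody-positive subjects to be recalled after the study. Section 1.3 reports arteritis in treated monkeys, most often in kidney and gut, and says it may indicate a risk of immune-mediated effects in patients. Post-dose creatinine, urinalysis and antibodies bear on that risk.

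The protocol already protects one sample against the same problem. The repeat biopsy is required if not yet done, whatever the calendar says. Viral and antibody samples have no such protection.

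**Working it through.** The protocol gives no figure to reproduce, so the check sets the waiver against the visit schedule.

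**Inputs (Section 3.5).** Day 0 samples fall on Day 0, or as early as Day -3 under the 72-hour allowance. Lab draws, with visit windows, fall on Days 6-8, 12-16, 19-23 and 26-30. Viral and antibody samples fall on Day 0 and then Day 28. Infusions in Cohorts 6-8 are on Days 0, 7, 14 and 21, each after that day's draw. The Day 22 visit has no routine labs.

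**Rule.** With D the day of the discontinuation visit and S the day of the latest sample of that type, the assessment is waived if D - S ≤ 14.

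**Viral tests and antibodies, all cohorts.**
- S = 0: waived if D ≤ 14.
- S = -3: waived if D ≤ 14 - 3 = 11.
- Later than that, and before the Day 28 visit, the baseline sample is too old and both must be collected. From Day 28 the latest sample is post-dose.

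**Labs before the Day 7 draw, all cohorts.** The longest interval is 8 - (-3) = 11 days, which is under 14. The waiver always applies, and the only labs are pre-dose.

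**Labs after the last infusion, Cohorts 6-8.** The longest possible gaps between consecutive draws are:

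| From | To | Gap (days) |
|---|---|---|
| Day 0 draw, earliest -3 | Day 7 draw, latest 8 | 11 |
| Day 7 draw, earliest 6 | Day 14 draw, latest 16 | 10 |
| Day 14 draw, earliest 12 | Day 21 draw, latest 23 | 11 |
| Day 21 draw, earliest 19 | Day 28 draw, latest 30 | 11 |

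Every gap is under 14. A subject dosed on schedule who leaves before the Day 28 draw therefore always has a lab set recent enough to trigger the waiver, and that set precedes the last infusion. From Day 7 on, it does follow an earlier infusion.

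**Labs, single-dose cohorts.** From the Day 7 draw on, every lab set is post-dose, so there is no gap.

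**With the added condition.** If a waived sample must also follow the most recent infusion, none of the pre-infusion samples above qualifies. No subject who attends the visit would then leave without post-dose labs, viral tests and an antibody sample.

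**Weight of one subject.** 1/4 = 25% of a planned cohort of four. Section 1.4 reports 17 subjects enrolled and escalation through Cohort 5, matching 1 + 4 × 4 = 17. A change would then act mainly on Cohorts 6-9, which have 33 - 17 = 16 planned subjects.

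**The case against.** The strongest reply is that few subjects are exposed to the rule. Sections 3.5 and 4.7 keep anyone who only stops drug on the full schedule, samples included, unless consent is withdrawn. That stands. The gap concerns only those who leave the study itself and still come to the exit visit. No wording can compel samples from someone who refuses them.

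A reader might infer that early leavers are the subjects most likely to have reacted. The documents do not say so, and the follow-up rule in Section 4.7 points the other way for those who stop drug after a reaction. A reader might also infer that every test can be skipped, or that labs are purely pre-dose throughout. Neither is supported. The biopsy has its own rule. PK and receptor occupancy are sampled half an hour after the Day 0 infusion. Labs are purely pre-dose only before the Day 7 draw.

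Other safety capture also remains. Adverse events and vital signs are recorded at every visit, infusion reactions trigger biomarker samples, medically significant abnormal labs are to be repeated, and serious events are followed to resolution. The waiver permits skipping and does not forbid collection.

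Finally, nobody has a scheduled post-dose viral or antibody sample before Day 28, and in the single-dose monkey study antibodies became more frequent at later time points. A negative result within two weeks is therefore weak evidence. That limits the value of the lost sample, but it is the only post-dose viral or antibody result such a subject would ever give.

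Leavers before Day 7 for non-safety reasons are not evaluable for safety and may be replaced. They still stay in all summaries under Section 5.3.

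**Conclusion.** The point holds within these limits. For subjects who leave the study and attend the discontinuation visit, the rule as written allows exit with:

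- only a pre-dose viral and antibody result if the visit falls by Day 14 (Day 11 with a baseline drawn 72 hours early), in all cohorts;
- only pre-dose chemistry, hematology and urinalysis if the visit precedes the Day 7 draw;
- in Cohorts 6-8, none of these labs after the last infusion if the subject leaves before the Day 28 draw.

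This assumes that two weeks means 14 days inclusive, that scheduled visits are attended within their windows, and, for the third item, that infusions were given on schedule. A subject whose infusions stopped earlier but who attended a later lab visit would have labs after the last infusion. The documents give no rate of early leaving, so the number affected cannot be estimated.

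The gap does not threaten the study. It is a stated rule that gives a poorer safety record than intended, in cohorts where each subject carries much of the information, and it is worth correcting.

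**What to change.** In both discontinuation visit lists of Section 3.5, in footnote a of Tables 3.5-1 and 3.5-2, and in Section 3.7, state that chemistry, hematology, urinalysis, viral tests and anti-MEDI-546 antibodies may be skipped only if they were performed within 2 weeks and after the subject's most recent infusion. Leave the waiver as it is for clinical scores, questionnaires and all other assessments, so that early leavers are not asked to repeat those within days of baseline. The biopsy rule needs no change.

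The cost is one sentence in each place and, for the few subjects concerned, at most one routine blood, urine and swab set at a visit that is already scheduled. A Cohort 6-8 subject who leaves after Day 14 and before the Day 28 draw would need only the routine labs in addition, because the viral and antibody samples are already required by then.

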3.6 Subject Evaluation Methods

3.6.1 Medical History

A complete medical history by body system will be completed during screening. History of allergies and anaphylaxis, viral reactivation events, previous manifestations of scleroderma, and previous treatment of scleroderma with potentially disease-modifying therapy will be included. On Study Day 0, the medical history will be reviewed and any changes from screening will be documented.

3.6.2 Physical Examination

Physical examinations will be performed at intervals designated in [Table 3.5-1](#) and [Table 3.5-2](#) and will include the following assessments: head, eyes, ears, nose, and throat; respiratory; cardiovascular; gastrointestinal, musculoskeletal; neurological; dermatological; lymphatic; endocrine system; body weight; and body height (screening only).

Medically significant changes from the screening physical examination will be considered AEs or SAEs and recorded as such on the source document.

3.6.3 Electrocardiogram

A 12-lead electrocardiogram (ECG) will be done at screening and at the end of study (Study Day 84 or 105) or at study discontinuation according to investigative site procedures. The principal investigator or qualified designee will review and indicate if the ECG is normal or abnormal. Any medically significant changes from the screening ECG will be recorded as an AE or SAE.

3.6.4 Chest X-ray

A chest X-ray (anterior/posterior and lateral) will be completed during the screening period. The chest x-ray may be substituted with documentation of a previous chest x-ray performed within the previous 6 months. A previous computerized tomography evaluation of the lungs may be substituted for the chest x-ray if performed within the last 6 months.

3.6.5 Pulmonary Function Tests

Pulmonary function tests will be performed at a qualified site according to American Thoracic Society/European Respiratory Society (ATS/ERS) guidelines (Miller, 2005) on study days indicated in Table 3.5-1 and Table 3.5-2. Both the absolute measurement for FVC and DL_{CO} and the percentage of predicted normal values (Hankinson, 1999; Hankinson, 2003) will be recorded; the predicted value will be interpolated from an extension of the curve when the subject's values are out of range (eg, too tall or too short).

